3. SAFETY ANALYSES

3.1 ADVERSE EVENTS AND SOLICITED SYMPTOMS

3.1.1 *Available data*

Unsolicited adverse events (AEs) are coded into system organ classes and preferred terms using the medical dictionary for regulatory activities (MedDRA). For each AE, start and stop dates and times are collected as well as severity (grade 1 to grade 5), a seriousness flag, an AE of special interest (AESI) flag (i.e. events which could have an autoimmune origin), treatment relatedness (both to treatment and challenge agent), action taken towards the study drug and outcome.

The following solicited symptoms will be collected:

- Day 1 to Day 7 following vaccination (patient diary):
 - Local symptoms: pain, redness, induration (swelling), warmth, pruritis (itching)
 - Systemic symptoms: feverishness, chills, fatigue, myalgia/arthralgia (muscle/joint pain), headache, nausea, malaise, temperature
- Day 1 to Day 11 following challenge (SSC):
 - Local symptoms: nasal congestion (blocked nose), runny nose, sneezing frequency, sinus pressure/pain or facial pain, sore throat, difficulty swallowing, teary/watery eyes, painful eyes, aversion to light, dry cough, productive (wet) cough, difficulty breathing/tight chest
 - Systemic symptoms: dizziness, head congestion, headache, muscle aches, feverish, chills or shivering, lack of appetite, felt cold, sweating, nausea, stomach ache, vomiting, diarrhoea, tiredness/weakness, sleeping more than usual, lymphadenopathy

The following symptoms will only be questions if at least 2 other symptoms with grade 2 or higher are present: nausea, stomach ache, vomiting, diarrhoea, tiredness/weakness, sleeping more than usual.

Solicited symptoms clearly not related to the treatment/challenge are captured as adverse events in the clinical database. Therefore, events captured as solicited symptoms in the clinical database are always considered (at least possibly) related to the treatment/challenge. Each symptom's severity is graded from 0 (absent) to 3 (grade 3 - severe), except for redness and temperature, which are reported in mm for longest diameter and °C respectively.

	Statistical Analysis Plan	
FLU010	Final analysis	Final 3.0 of 15JUN2020

3.1.2 *Derivation rules*

Redness and temperature will be graded as follows:

Grade	Redness (mm)	Temperature (°C)
Normal (0)	< 25	< 38.0
Grade 1	25-50	38.0-38.4
Grade 2	51-100	38.5-38.9
Grade 3	> 100	39.0-40.0
Grade 4		> 40.0

Treatment-emergent adverse events (TEAE) are defined as AEs starting during or after first administration of any study drug. Treatment-emergent (TE) solicited symptoms are defined as solicited symptoms reported from Day 1 on.

Based on their start date and time, AEs will be allocated to the phase during which they started. Each AE will therefore be reported in only one phase. (See section 5.2.1 for further information about study phases). In case the AE start date or time is incomplete or missing and the AE could consequently be allocated to more than one phase, the AE will be allocated to the treatment phase unless the available parts of the AE start or stop date(time) provide evidence for allocating to the non-treatment phase (screening / challenge / follow-up).

Some of the final safety presentations will include the number of reported events during the trial's analysis phases, not only the number of subjects who reported at least one event. Any change in AE severity is reflected by a new AE record being entered in the safety database. As such, the number of events could be inadvertently overreported due to the way in which AE records are captured within the safety database.

Overlapping/consecutive (unsolicited) events are defined as events occurring in the same subject with the same MedDRA preferred term and primary system organ class that have at least one day overlap or for which the start date of an event is one day

	Statistical Analysis Plan	
FLU010	Final analysis	Final 3.0 of 15JUN2020

after the end date of the preceding event. Overlapping/consecutive events may be combined into one AE or not, according to the following rules:

- In case overlapping/consecutive events start within a single phase (see section 5.2.1 for further information about study phases.), they are considered as one and the same AE. The individual events that contribute to this AE are retained as individual records in the ADaM database but are assigned the same onset, end, phase and total duration. They are counted/presented as one event in TLFs.
- In case overlapping/consecutive events start both in the challenge phase and in the follow-up phase, they are allocated to the active phase only (challenge phase) and are considered as one and the same AE. The individual events that contribute to this AE are retained as individual records in the ADaM database but are assigned the same onset, end, phase and total duration. They are counted/presented as one event in TLFs.
- In all other cases, overlapping/consecutive events are allocated to their respective phase and are considered as separate AEs. Examples of this are events starting both in the screening phase and in the vaccination phase or both in the vaccination phase and in the challenge phase.
- Remarks:
 - Events can only be combined into one and the same AE if both start dates and the stop date of the first event are known.
 - In case the completely missing end date is imputed (for phase allocation), this date is also considered as a complete date.
 - Time of day is not considered when determining overlap of events, only start and stop dates.

Below example illustrates above rules. Both events occur in the same subject, for whom the follow-up phase starts on 07SEP2019T00:00.

SDTM:

AEPT	AEREL	AESEV	AESTDT	AEENDTC
HEADACHE	Y	1	06SEP2019T19:30	07SEP2019T08:40
HEADACHE	N	3	07SEP2019T10:00	07SEP2019T15:20

ADaM:

AEPT	AEREL	AESEV	AESDTM	AEEDTM	AEDUR	APHASE
HEADACHE	Y	1	06SEP2019T19:30	07SEP2019T15:20	2	CHALLENGE
HEADACHE	N	3	06SEP2019T19:30	07SEP2019T15:20	2	CHALLENGE

AE tables:

	Number of subjects	Number of events
Grade ≥ 3 AEs	1	1
Related AEs	1	1
Related Grade ≥ 3 AEs	0	0

	Statistical Analysis Plan	
FLU010	Final analysis	Final 3.0 of 15JUN2020

Consecutive solicited events are defined as events occurring in the same subject with the same symptom name that occurs on consecutive days. These are combined into one AE, according to the following rules:

- Only the assessment day, as identified by QS.VISIT is used. For solicited events after challenge, am/pm information is not taken into account for the combination of events.

Day 3 am	Day 3 pm	Day 4 am	Day 4 pm	Day 5 am	Counted as
grade 1	grade 0	grade 0	grade 2	grade 1	1 event of grade 2
grade 1	grade 1	grade 0	grade 0	grade 2	2 events

- In case of missing intermittent assessments, it is assumed the event is still present on the missing days.

Treatment relatedness will be dichotomised as follows in tables:

- Treatment related: at least possibly related or missing
- Not treatment related: not related, unlikely

AE onset and duration will be calculated as follows when start and stop dates are fully known:

- AE onset day (vs. vaccination) = AE start date – date of vaccination + 1 day
- AE onset day (vs. challenge) = AE start date – date of challenge + 1 day
- AE duration (days) =
 - AE end date – AE start date + 1 day
 - study discontinuation/completion date – AE start date + 1 day (when the AE start date is fully known but the AE is not resolved at the end of the study)

In this case the duration will be presented as “>x days”, x being the duration of the AE calculated by the end of the study.

3.1.3 *Presentation of results*

Tables will present TEAEs only. Pre-treatment AEs and follow-up AEs will only be listed. All tables will be presented by analysis phase (vaccination / challenge).

Analysis phases are defined in section 5.2.1.

	Statistical Analysis Plan	
FLU010	Final analysis	Final 3.0 of 15JUN2020

An overview table will show the number and percentage of participants with at least one event and the number of events for the following:

- TEAEs
- Solicited symptoms
- TEAEs or solicited symptoms
- Local solicited symptoms
- Local grade 3 solicited symptoms
- Systemic solicited symptoms
- Systemic grade 3 solicited symptoms
- Treatment-emergent AESI
- Serious TEAEs
- Non-serious TEAEs
- Grade ≥ 3 TEAEs
- Treatment-emergent grade ≥ 3 laboratory toxicity (see section 3.2.2)
- Fatal TEAEs
- TEAEs related to treatment (vaccination phase)
- TEAEs related to challenge (challenge phase)
- Serious TEAEs related to treatment (vaccination phase)
- Serious TEAEs related to challenge (challenge phase)
- Grade ≥ 3 TEAEs related to treatment (vaccination phase)
- Grade ≥ 3 TEAEs related to challenge (challenge phase)
- TEAEs for which the study was discontinued

Summary tables by MedDRA system organ class and preferred term will show the number and percentage of subjects with at least one event. The table of TEAEs will additionally show the number of events.

Separate tables will be prepared for the following:

- TEAEs
- Treatment-emergent AESI
- Serious TEAEs
- Non-serious TEAEs
- Grade ≥ 3 TEAEs
- TEAEs by worst severity
- Treatment related TEAEs
- Serious treatment related TEAEs
- TEAEs for which the study was discontinued

A summary table by symptom will show the number and percentage of participants with at least one symptom, overall, by type (local/systemic) and by symptom. The

	Statistical Analysis Plan	
FLU010	Final analysis	Final 3.0 of 15JUN2020

table of solicited symptoms will additionally show the number of events. Distinct tables will be prepared for the following:

- solicited symptoms
- grade 3 solicited symptoms
- solicited symptoms by worst severity

All AEs, including pre-treatment events will be listed. Separate listings will be prepared for serious AEs, AEs for which the study was discontinued and fatal AEs. A listing showing all coding information will be prepared as well. Listings will also be prepared for solicited symptoms and grade 3 solicited symptoms.

More details can be found in the list of tables and listings (see section 8)

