Nasal swabs for influenza virus are collected twice a day (at least 8 hours apart) from Day 2 to Day 10 following intranasal challenge, which are tested for influenza PCR and culture. Symptoms of influenza-related infection will be collected from Day 1 to Day 11 of challenge, as will total nasal tissue weight.

Efficacy: Total viral area under the curve (vAUC) for virologic shedding as measured by quantitative PCR (qPCR) for MVA-NP+M1 vs. Placebo groups.

Secondary endpoints include:

- Incidence in each group (MVA-NP+M1 and saline Placebo) of laboratory-confirmed ILI (qPCR or culture)
- Total AUC for total symptom score for MVA vs. Placebo
- Total days of fever for MVA-NP+M1 vs. Placebo
- Total mucus weight for MVA vs. Placebo
- Correlation of T cell responses (as defined by ELISpot assay) to the primary endpoint, symptom scores, and influenza incidence
- The attack rate, defined as percentage of inoculated participants with at least two positive swabs as determined by qPCR

Exploratory endpoints

- Time to start; time to peak and duration of qPCR and quantitative culture results
- Time to start, time to peak, and duration for total symptoms for MVA vs. Placebo
- Severity of individual symptoms for MVA-NP+M1 vs. Placebo

- Correlation of antigen specific T cell phenotypes to the primary endpoint, symptom scores, and influenza incidence
- Effect of vaccination on the antibody responses to influenza following the intranasal challenge
- Transcriptional response to vaccination and viral challenge assessed by deep sequencing of RNA
- Potential assessment of epigenetic responses of T-Cells during the study.

Safety

- Frequency and severity of participant-recorded local and systemic adverse events recorded for the 7 days following vaccination
- Frequency and severity of non-solicited adverse events captured throughout the study after vaccination
- Frequency and types of serious adverse events
- Severity of adverse events in each study group following intranasal challenge with H3N2

Statistical Methods:

Sample size: determined by the challenge cohort of N=134

Immune response:

Primary immune endpoint will be the T cell response measured by ELISpot and recorded as the mean spot forming units per million peripheral blood mononuclear cells (PBMCs) in the peptide-stimulated wells minus the mean dimethyl sulfoxide (DMSO) control wells for the given sample.

Efficacy:

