9.1.3 Safety Data

Safety parameters will be tabulated and analysed descriptively.

Adverse Events

The original terms used in the eSource documents by Investigators to identify AEs will be fully described and coded according to the Medical Dictionary for Regulatory Activities (MedDRA).

The reported AEs will be allocated to phases based on their start date. All AEs will be listed. All AEs with onset after Day 1 of vaccination will be summarized by treatment group. Summaries, listings, and narratives may be provided, as appropriate. Summaries will include at a minimum SAEs, and for both solicited and unsolicited AEs, the severe (grade 3+ events), related AEs, and AEs following challenge.

Clinical Laboratory Tests

Each continuous biochemistry and haematology laboratory test will be evaluated by means of descriptive statistics (i.e., number of participants, mean, SD, median, minimum, and maximum) on the actual values, at each assessment time point and by vaccination group.

Relative changes in clinical laboratory test values compared to values at baseline will be evaluated according to the appended toxicity scale or in accordance with the normal ranges of the clinical laboratory (below, within, or above normal range) for parameters for which no toxicity grades are defined.

A listing of participants with any clinical laboratory test result outside the reference ranges will be provided.

Vital Signs

Pulse rate, temperature, SBP, and DBP will be evaluated by means of descriptive statistics (actual values and changes from Day 1 to Day 2 of the vaccine phase and from Day 1 of the challenge phase and frequency tabulations at each assessment time point and by vaccination group).

Pulse oximetry will be measured during the entire challenge phase.

The percentage of participants with values beyond clinically important limits (as defined in the Toxicity Tables) will be summarized.

Electrocardiogram

ECG variables will be evaluated by means of descriptive analysis by the Investigator at each assessment time point.

The percentage of participants with ECG abnormalities will be summarized.

The ECG variables that will be analysed by electronic capture from the ECG include heart rate, PR interval, QRS interval, QT interval.

Physical Examination

Abnormal findings in physical examination will be listed.

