5.2 PHASES AND TIME POINTS

5.2.1 *Phases*

All events and assessments will be allocated to phases.

Phase	Start	End
Screening	Date of signing the ICF, with 00:00 added as time part	Vaccination date(time) – 1 minute
Vaccination	Vaccination date(time)	Challenge date(time) – 1 minute
Challenge	Challenge date(time)	End date of Day 28 post-challenge visit, with 23:59 added as time part
Follow-up	End of challenge phase + 1 minute	Date of last contact, with 23:59 added as time part

Per definition, and for each subject, the last available phase ends on the date of last contact (or the cut-off date for the topline analysis), with 23:59 added as time part.

AEs will be allocated to phases as described in section 3.1.2. All other assessments will be allocated to phases based on the assessment date(time).

In case of (partially) missing date(time) fields which cannot be allocated to a phase based on the available date(time) information, the visit label will be used to allocate to the correct phase. If this is not possible (unscheduled visits or visits on a turning point between phases), assessments will be allocated to the vaccination phase unless the available parts of the assessments start or stop date(time) provide evidence for allocating to the challenge/screening/follow-up phase.

5.2.2 *Baseline and change from baseline*

Baseline will be defined by phase.

The vaccination baseline value is the last available and non-missing value before the first administration of any study drug and will be used for data collected during the vaccination period.

The challenge baseline value is the last available and non-missing value before the administration of challenge inoculation and will be used for data collected during the challenge period.

Change from baseline is defined as follows:

Change from baseline at time point t = value at time point t – baseline value.

	Statistical Analysis Plan	
FLU010	Final analysis	Final 3.0 of 15JUN2020

5.2.3 *Relative day*

Relative days (DY) will be calculated both with respect to the vaccination and to the challenge, according to the following rule:

- Concerned date < reference date: DY = concerned date – reference date
- Concerned date \geq reference date: DY = concerned date – reference date + 1

The reference dates are the vaccination date and the date of challenge.

5.2.4 *Analysis visits*

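### SAP 3.1.3 lists but does not tabulate adverse events that start in the follow-up phase, contrary to protocol 9.1.3, and SAP section 6 does not declare the change

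*SAP*

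**What the plan says.** **Protocol.** Section 9.1.3 sets two duties, to list all adverse events and to summarise them. On the second it says "All AEs with onset after Day 1 of vaccination will be summarized by treatment group" and "Summaries will include at a minimum SAEs", and it also names severe and related events. It gives no end date. The synopsis has as a safety endpoint "Frequency and severity of non-solicited adverse events captured throughout the study after vaccination". Section 7.2.2 monitors events to about 27 days after challenge or 6 months after vaccination, whichever is longer. Section 10.1 has events of special interest recorded for the whole study.

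**SAP.** Section 3.1.2 gives an open-ended definition: "Treatment-emergent adverse events (TEAE) are defined as AEs starting during or after first administration of any study drug". Section 3.1.3 promises tables of treatment-emergent events, split by vaccination and challenge phase, and then says "Pre-treatment AEs and follow-up AEs will only be listed". Section 5.2.1 ends the challenge phase at "End date of Day 28 post-challenge visit, with 23:59 added as time part" and opens the follow-up phase one minute later. It also provides that "for each subject, the last available phase ends on the date of last contact". Sections 6.1 and 6.2 declare no change to the planned analysis.

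**The concern.** An event that starts in the follow-up phase is treatment-emergent under SAP 3.1.2 and falls under the protocol's requirement for a summary by arm. SAP 3.1.3 nevertheless keeps it out of the tables. The titles of Tables 14.3.1.1 to 14.3.1.10 mention no such cut-off, so a reader would take the counts as complete.

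The affected interval is the one that the Month 6 call adds. Under protocol 7.1.3 the call asks about interim SAEs, and for challenged participants it applies only if it falls later than 27 days after challenge. At stake are the by-arm counts of SAEs and of events of special interest (Guillain-Barré syndrome, Bell's palsy, myocarditis, Stevens-Johnson syndrome), which bear on the stated safety endpoints.

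The rule also treats participants differently. Someone never challenged has no challenge or follow-up phase, so the vaccination phase runs to last contact. A late event is then tabulated for that person, while the same event on the same day in a challenged participant may not be.

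**Working it through.** **1. What is excluded.** Events are allocated by start date (SAP 3.1.2), not by the contact at which they are reported.

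| Event in a challenged participant | In a table? |
|---|---|
| Reported at Month 6, started before the challenge phase ended | Yes |
| Starts in follow-up; overlaps or directly follows a challenge-phase event of the same term | Yes, counted under challenge |
| New onset in follow-up, known start date | No, listed only |

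**2. The plan's own figure.** The documents give no figure for the untabulated share. Their only figure on safety precision is the synopsis statement of a 93% chance of seeing at least one SAE of 3% incidence. The formula is 1 − 0.97^n:

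- n = 93 (active arm vaccinated): 94.1%
- n = 80 (active arm challenged): 91.3%
- n = 134: 98.3%; n = 155: 99.1%

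The figure therefore fits an active-arm count and not the whole trial.

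**3. Untabulated share of the window.** Let c be the days from vaccination to challenge. Protocol 7.1 allows c from 6 weeks to under 6 months. It puts the post-challenge visit at c + 27 (±3) and the Month 6 contact at 180 (±14).

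Untabulated share = max(0, 180 − (c + 27)) / 180

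| c (days) | Weeks | Untabulated days | Share |
|---|---|---|---|
| 42 | 6 | 111 | 61.7% |
| 56 | 8 | 97 | 53.9% |
| 63 | 9 | 90 | 50.0% |
| 84 | 12 | 69 | 38.3% |
| 126 | 18 | 27 | 15.0% |
| 153 | about 22 | 0 | 0% |

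With the visit windows applied, the 6-week share ranges from 56.6% to 66.0%. The share exceeds one half only if c is below 63 days, or below 53 to 73 days depending on the windows.

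**4. Illustration for SAEs in the active arm.** Assumptions: 3% incidence over 180 days at a constant rate, 80 challenged and 13 unchallenged (protocol Table 2), the unchallenged followed to Month 6, and everyone challenged at the same c. With f = min(1, (c + 27)/180):

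P(at least one SAE reaches a table) = 1 − (1 − 0.03f)^80 × 0.97^13

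- All events tabulated (f = 1): 94.1%
- c = 42, f = 0.383: 73.3%
- c = 63, f = 0.500: 79.9%
- c = 84, f = 0.617: 84.9%
- c ≥ 153, f = 1: 94.1%, no loss

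**5. Unchallenged participants by arm.** Planned: 13/93 = 14.0% active and 8/62 = 12.9% placebo, 21 of 155 in all.

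**The case against.** The strongest reply is that this is a matter of presentation. Safety analysis is descriptive, and every adverse event is listed. SAEs, fatal events and events leading to discontinuation have their own listings (SAP 3.1.3 and 8.2), and listings are ordered by treatment (SAP 5.4.3). With 155 participants, a few late SAEs could be counted by arm by hand. It stands that nothing is lost from the record. The reply does not meet the protocol, which asks for a summary in addition to a listing; its later permissive wording on summaries, listings and narratives does not cancel that. The reply is weakest for events of special interest, which are flagged in the data but have no listing of their own.

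A second reply is that the vaccination phase varies in length with the challenge date in any case, that Table 14.1.1.4 reports phase durations, and that unchallenged participants are spread almost evenly across arms. This stands. A reader might infer that unequal windows bias the comparison of arms, but the planned numbers do not support that.

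A third reply is that the Month 6 call is aimed at SAEs, so tabulating all follow-up events would mix intensities of ascertainment. This stands for non-serious events and calls for a footnote. It is no reason to leave out SAEs.

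**Conclusion.** The inconsistency is real. As written, the SAP gives incomplete by-arm counts of new-onset SAEs and events of special interest in challenged participants, conflicts with protocol 9.1.3 and with its own definition of treatment-emergent, and does not say so in section 6. Up to 134 of 155 participants could be affected.

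The size depends on when participants are challenged: from about 62% of the 180-day window at 6 weeks to nil from about 22 weeks. SAP 4.6.1 gives only a minimum interval and the cohort spacing, so no typical share can be stated. The probabilities in the illustration rest on an assumed constant rate and a common challenge day.

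Three stronger readings are tempting, and the documents do not support them:

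- That more than half of the safety window goes untabulated in general. This holds only for challenge before about Day 63.
- That every event after the Day 28 post-challenge visit is left out. Same-term events that overlap or directly follow a challenge-phase event are counted.
- That nothing found at Month 6 reaches a table. Events that began before the challenge phase ended do.

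The primary endpoint is untouched. The point concerns the completeness and consistency of the safety tables, and it is worth correcting because the correction is cheap.

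**What to change.** - In SAP 3.1.3, delete the listing-only rule for follow-up events, keep it for pre-treatment events, and amend the sentence that limits the tables to two phases.
- Add a column by arm running from vaccination to last contact to Tables 14.3.1.1 to 14.3.1.4 (overview, treatment-emergent, special interest, serious) and 14.3.1.6 to 14.3.1.8 (grade 3 or more, related, serious related). The last three are needed because protocol 9.1.3 names severe and related events. This column puts challenged and unchallenged participants on the same footing. A separate follow-up column is optional and would not do that alone.
- Add a footnote that the Month 6 call is directed at SAEs, so non-serious events may be less fully ascertained in follow-up.
- If the sponsor keeps the present rule, declare and justify it in SAP section 6 as a departure from protocol 9.1.3.

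The cost is SAP wording and table programming. The data are already collected.
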